8. ANALYSIS SETS

The safety analysis set includes all randomized subjects who receive treatment with the study treatment (iovera^o or RFA). All analyses based on the safety set will be by actual treatment received.

The efficacy analysis set will include all randomized subjects who receive treatment with the study device. All analyses based on the efficacy analysis set will be by randomized treatment regardless of the actual treatment received.

The per-protocol analysis set will include all subjects in the efficacy analysis set who do not have any key protocol deviations. All efficacy analyses based on the per-protocol analysis set will be by randomized treatment regardless of the actual treatment received. All analyses based on the per-protocol analysis set will be by randomized treatment regardless of the actual treatment received.

9. STATISTICAL METHODS OF ANALYSIS

9.1. General Principles

The statistical analyses will be reported using summary tables, listings, and figures (TLFs). All analyses and tabulations will be performed using SAS Version 9.4 or later. Continuous variables will be summarized using descriptive statistics [sample size (n), mean, standard deviation (SD), minimum, median, and maximum]. Categorical variables will be tabulated with the number and percentage of unique subjects. Unless otherwise noted, percentages will be calculated using the number of subjects in the respective treatment group and analysis set as the denominator and presented with only those categories appearing in the data.

Individual subject data will be provided in listings. All listings will be sorted by treatment, site, subject, and, if applicable, collection date and time.

9.1.1. Handling Missing Values

9.1.1.1. NRS Pain Intensity Scores from Day of iovera^o/RFA treatment from 24hr after treatment to Day X (7, 15, 30, 60, 90, 120, 150, 180, 210, 240, 270, 300, and 360)

For subjects who drop out of the study early because of a related AE or lack of efficacy, their later missing timepoints will be imputed using worst-observation-carried-forward (WOCF) method, in which their worst observation since the first daily pain assessment will be carried to Day 15 (or subsequent days), For subjects dropping out early for any other reason, last-observation-carried-forward (LOCF) imputation will be used.

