Given the COVID-19 pandemic, the subject must be medically fit/cleared for treatment by the investigator. If there is a concern about a subject's recent or potential exposure to COVID-19, or if the subject is not medically fit/cleared for treatment due to suspected COVID-19 illness/symptoms (or other serious illness), the subject must be excluded per *Exclusion criterion #4*.

Study Device:

Name: iovera° System

Duration of Subject Participation in Study:

Participation will begin at the signing of the study ICF. No more than 30 days should pass between signing of the ICF and the iovera^o or RFA treatment procedure. Subjects will be followed up for 360 days (\pm 7 days) after iovera^o or RFA treatment. Therefore, subjects may participate in the study for up to 392 days.

Study Stopping Rules

The study may be terminated if the Investigator, or officials from regulatory authorities identify conditions during the study that indicate so.

The Investigator will review all serious adverse device effects and serious adverse events (SAEs) reported from the clinical study on an ongoing basis and in real time (i.e., as the events are reported). The Investigator will be responsible for temporarily halting the study if the type, frequency, or seriousness/severity of such events suggests a potential threat to the safety of the study participants. If such action is taken, a thorough review of all available data will be conducted. Based on the results of this review and discussions with the Investigator and/or regulatory authorities as warranted, the study may be restarted or permanently terminated.

In addition, any death will be thore	oughly reviewed, and a	appropriate action taken.	

Removal of Subjects from Therapy or Assessment

Every reasonable effort will be made to maintain subject compliance and participation in the study. Reasons for discontinuation of any subject from the study will be recorded.

If any clinically significant event or condition is uncovered during the study period that might render the subject medically unstable or compromise the subject's post-treatment course, the subject will be withdrawn from the study and the event or condition will be reported as an AE or SAE.

If a subject withdraws from the study and has an ongoing AE, every effort will be made to follow up on such events until satisfactory resolution is obtained or further follow-up is otherwise no longer warranted.

Withdrawal Secondary to Adverse Events

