The severity (or intensity) of an adverse device event or AE should be categorized using the following guidelines:

- Mild: An adverse device event or AE that is easily tolerated by the subject, causing minimal discomfort and not interfering with everyday activities.
- Moderate: An adverse device event or AE that is discomforting and interferes with normal everyday activities.
- Severe: An adverse device event or AE that prevents normal everyday activities.

The term "severe" is often used to describe the intensity (severity) of a specific event (as in mild, moderate, or severe myocardial infarction); the event itself, however, may be of relatively minor medical significance (such as severe headache). This is not the same as "serious," which is based on subject/event outcome or action criteria usually associated with events that pose a threat to a subject's life or functioning. Seriousness (not severity) serves as a guide for defining regulatory reporting obligations.

Relationship of Adverse Device Effects to Study Device and Adverse Events to Drugs The Investigator is required to assess the relationship of the adverse device event, malfunction, and/or AE to study device and/or medication received for each occurrence after careful medical consideration on a case-by-case basis. The determination of the causal relationship to the study device and/or drug(s) will be made using the definitions below:

- Unrelated: A causal relationship can be easily ruled out (e.g., based on the temporal sequence, absence of a reasonable pathophysiological mechanism, or direct evidence of actual cause).
- Unlikely: A clinical event with a temporal relationship to study device and/or drug(s) administration which makes a causal relationship improbable and in which other drugs, chemicals, or underlying disease provide a plausible explanation;
- Possible: A clinical event with a reasonable time sequence to administration of the study device and/or drug(s) but which could also be explained by a concurrent disease or other drugs or chemicals;
- Probable: A clinical event with a reasonable time sequence to administration of the study device and/or drug(s) unlikely to be attributed to a concurrent disease or other drugs or chemicals and which follows a clinically reasonable response on withdrawal (dechallenge); or

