9.7.2. Methods of Analysis

For Primary and Secondary Efficacy Analyses, descriptive statistics (number of subjects, mean, SD, median, minimum, and maximum) will be provided for continuous data. Tabulations (number and percentage of subjects) by category will be provided for categorical data. All efficacy analyses will be performed on the efficacy analysis set.

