9.7.2.1. Primary Efficacy Analysis

9.7.2.1.1. NRS "average pain over past 24 hours" Intensity Score scores from first pain assessment post-treatment (Day 1) to Day 360

The primary analysis of the primary efficacy endpoint will compare the iovera^o and RFA group. The superiority of iovera^o to RFA will be evaluated based on the following null hypothesis and alternative hypothesis:

H₀: iovera^o is not superior to RFA with respect to mean of NRS pain intensity scores at Day 360

H_a: iovera^o is superior to RFA with respect to mean of NRS pain intensity scores at Day 360

A two-sided hypothesis test will be performed at $\alpha=0.05$ level of significance comparing EXPAREL and bupivacaine HCl as follows:

- If the two-sided p-value for the least squares mean treatment difference in NRS at Day 360 (iovera^o- RFA) is >0.05 , then the superiority of iovera^o to RFA is not achieved.
- If the p-value for the least squares mean treatment difference in NRS at Day 360 (iovera^o- RFA) is ≤ 0.05 , then the superiority of iovera^o to RFA is achieved.

Least Squares Means (LSM) of “average pain over 24 hours” at Day 360 will be calculated for each subject. LSM for “average pain over 24 hours” at Day 360 will be summarized by treatment group, and overall.

To test for significant differences between iovera^o and RFA group, a Linear Regression Model with adjustment of baseline NRS, sex, and tobacco status was used. The LS means for each treatment group, two-sided 95% CI for the LS mean difference, and p-value will be presented.

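### Missing NRS scores are handled only by LOCF or WOCF, chosen by dropout reason, with no sensitivity analysis behind the Day 360 comparison; a cheap SAP addition would cover this.

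*SAP*

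**What the plan says.** SAP section 9.1.1.1 gives two rules for NRS scores missing after early dropout. The first is for subjects who leave "because of a related AE or lack of efficacy, their later missing timepoints will be imputed using worst-observation-carried-forward (WOCF) method". The value used is defined by "their worst observation since the first daily pain assessment will be carried to Day 15 (or subsequent days". The second covers everyone else: "For subjects dropping out early for any other reason, last-observation-carried-forward (LOCF) imputation will be used". The section heading lists the visits as "24hr after treatment to Day X (7, 15, 30, 60, 90, 120, 150, 180, 210, 240, 270, 300, and 360". Day 330 is absent, although Protocol Table 2 schedules a call then. Scores missed by subjects who stay in the study have no rule.

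SAP section 9.7.2.1.1 tests superiority of iovera over RFA on average pain at Day 360, two-sided at 0.05. For this, "a Linear Regression Model with adjustment of baseline NRS, sex, and tobacco status was used". Section 9.7.2.2.1 repeats the analysis for Days 30 and 180. Section 9.7.2 adds: "All efficacy analyses will be performed on the efficacy analysis set". Section 8 defines a per-protocol set, but section 9.7 assigns no analysis to it. No mixed model, multiple imputation, observed-case or tipping-point analysis appears in the readable text, and the protocol's Statistical Methods give no missing-data method.

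The protocol (Removal of Subjects from Therapy or Assessment) says: "Reasons for discontinuation of any subject from the study will be recorded". On adverse events it says: "The Investigator is required to assess the relationship of the adverse device event, malfunction, and/or AE to study device". Neither document describes masking of subjects or investigator. The only blinded step is the review of protocol deviations in SAP section 9.3.

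Two further passages bear on the point. The protocol's Statistical Methods and SAP section 10 both say that efficacy is not the aim and that there will be no formal hypothesis testing. Protocol, Replacement of Subjects, lets subjects be replaced when their safety or clinical outcome data are incomplete.

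**The concern.** Follow-up lasts 12 months. LOCF can place a score from the first weeks at Day 360, and WOCF can place one from the first days after the procedure there. Neither estimates Day 360 pain unless pain is stable.

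The choice between the two depends on a recorded reason and, for adverse events, on the investigator's relatedness rating. Two subjects with identical scores can therefore receive different Day 360 values. With 15 subjects per arm, a few dropouts are enough to move the estimate.

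Section 9.7.2.1.1 turns that estimate into a statement that superiority is or is not achieved. The pilot is also meant to inform the sample size of a full trial. With a single rule and nothing beside it, a reader could not tell a treatment difference from a dropout pattern.

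**Working it through.** **Inputs.** From the documents: 15 per arm, Day 360 as the tested time point, two-sided 0.05, adjustment for baseline NRS, sex and tobacco. Dropout rate, SD and pain course are not given, so all of these are assumed below. The plan states no figure that could be reproduced first.

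**Step 1: arithmetic.** If k_A and k_B subjects are imputed and the mean imputation error is e points, the difference shifts by (k_A − k_B) × e / 15.
- Three more dropouts in one arm, e from 1 to 4: 3 × 1/15 = 0.20 to 3 × 4/15 = 0.80.
- Four more (5 vs 1): 0.27 to 1.07.
- Reason coding: moving two dropouts in one arm between WOCF and LOCF, with a gap of 2 to 5 points between the two values, shifts the difference by 2 × 2/15 = 0.27 to 2 × 5/15 = 0.67.

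**Step 2: simulation of the SAP rule, no true difference.** Assumed: between- and within-subject SD 1.6 each; mean NRS 4.0 on Days 1–6, 3.0 on Days 7–15, 2.5 on Days 30–90, rising to 5.0 at Day 360; first missed visit uniform over Days 30–360; 3000 trials per case (Monte Carlo SE about 0.016). Negative means that arm A looks better.

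| Dropout, A vs B | Imputation | Shift at residual autocorrelation 0 / 0.5 / 0.8 per 30 days |
|---|---|---|
| 33% vs 7% | all LOCF | −0.40 / −0.39 / −0.39 |
| 33% vs 7% | all WOCF | +0.37 / +0.09 / −0.02 |
| 20% vs 7% | all LOCF | −0.19 (at 0) |
| 20% vs 7% | all WOCF | +0.19 (at 0) |
| 20% vs 20% | 25% vs 75% of dropouts coded to WOCF | −0.27 / −0.15 / −0.11 |
| 20% vs 20% | same reasons | about 0 |

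Hand check of the first row. Taking the rise from Day 90 to Day 360 as a straight line, the mean at the last observed visit, averaged over the 12 possible dropout times, is 40.5/12 = 3.375. The mean carry-forward error is 5.0 − 3.375 = 1.625, and 4/15 × 1.625 = 0.43. This is close to 0.40; scores bounded at 0 account for some of the gap. For 20% vs 7%, 2/15 × 1.625 = 0.22, against 0.19.

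The false-positive rate was 0.049–0.052 when balanced and 0.072–0.080 at 33% vs 7% with LOCF. A separate simulation (pain from 3 at Day 30 to 5.5 at Day 360, last observation Day 30 to 180, 8000 runs) gave −0.38 and 0.077 at 30% vs 10% with LOCF.

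The result depends on the pain course. With flat pain, LOCF gives +0.01 and WOCF +0.70. If the arms wane differently (true difference −1.90, 20% dropout in each, half WOCF), the rule is off by +0.31 even though dropout is equal.

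**Step 3: check on the remedy.** A likelihood-based repeated-measures model on the observed visits had bias of +0.02 to +0.03 in the 33% vs 7% cases. Those figures come from a subject intercept with first-order autoregressive errors and constant variance. That structure fails if subjects differ in how fast pain returns. With an assumed SD of 2.5 for that variation at Day 360, its false-positive rate was 0.12–0.14 (mean SE 0.91–0.92 against a true SD of 1.16–1.22), compared with 0.05–0.07 for the SAP regression with LOCF. Adding a random slope brought it to 0.07–0.08. These last runs used 400 trials per case, so the Monte Carlo SE near 0.05 is √(0.05 × 0.95/400) = 0.011.

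**The case against.** The strongest reply is that this is a pilot. The protocol and SAP section 10 both renounce formal testing, so an inferential model may be out of place. That stands in part. Those statements conflict with SAP section 9.7.2.1.1, which plans a test and a verdict. If the conflict is settled in favour of description, the stakes fall, but descriptive Day 360 means that use imputed scores are still affected.

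A second reply is that the magnitudes are assumed and modest. That also stands. The estimate has an SD of about 0.8 in these scenarios, and root mean squared error is about the same for both approaches when pain rises to 5.0 (0.81–0.93 for the rule, 0.84–0.88 for the model). LOCF does better than the model when pain is flat. The gain is mainly less bias, not more precision. A 33% dropout rate may be pessimistic: the protocol keeps willing subjects in follow-up, and most contacts are by telephone.

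A reader might infer that the rule favours iovera, or that reasons will be coded to suit one arm. The documents support neither. The direction depends on which arm loses more subjects, for what recorded reason, and on the pain course; absence of described masking is not evidence of biased coding. A reader might also infer that replacing subjects removes treated patients from the denominators. SAP section 8 keeps treated subjects in the safety and efficacy sets. Finally, SAP section 9.6.4 on study success is redacted, so no effect on those criteria can be claimed.

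**Conclusion.** The point holds as a cheap improvement. The only readable NRS missing-data rule depends on dropout reason, feeds the Day 360 comparison directly, and has no sensitivity analysis beside it. Under assumed pain rising to 5.0 by Day 360, the shift is about 0.2 points at 20% vs 7% dropout and 0.4 at 33% vs 7% when all dropouts share one imputation method. Under WOCF it shrinks at higher autocorrelation, and it is about 0 when rates, reasons and pain course match.

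The documents do not support saying that the result will be biased, or that one particular model must replace the planned analysis. The constant-variance repeated-measures model can raise false positives more than the rule it would replace. The protocol also does not say that the Day 360 difference will drive the later sample size, so an effect there is possible but not established.

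**What to change.** In the SAP:
- Add a REML repeated-measures analysis of observed average-pain scores at the scheduled visits from Day 7 to Day 360, including Day 330. Terms: treatment, visit, treatment-by-visit, baseline average NRS, sex and tobacco. Use a covariance that lets variance grow over time, for example a random intercept and slope in days, not a constant-variance intercept-plus-autoregressive structure.
- Report the Day 30, 180 and 360 differences with 95% CIs beside the LOCF/WOCF result. Do not declare superiority from LOCF/WOCF alone if the two disagree.
- Add a shift analysis that ignores dropout reason: 0, +1 and +2 NRS points on dropouts' unobserved scores, in both arms and in each arm alone. With 5 and 1 dropouts, +1 and +2 in both arms move the difference by 4/15 = 0.27 and 8/15 = 0.53; in the five-dropout arm alone, by 5/15 = 0.33 and 10/15 = 0.67.
- Report numbers treated and observed, with dropout reasons, by arm and visit.
- Reconcile section 9.7.2.1.1 with section 10 and the protocol on formal testing.

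Secondary point: keep any replaced treated subject in the analysis sets and in the completeness report, because feasibility of the outcome measurements is itself a study aim.

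The cost is SAP wording, with no new data. Downsides: the model relies on dropout being at random given the observed data. The estimate has a slightly larger SD (0.84–0.88 vs 0.81–0.84, measured with the simpler covariance). Tests remain mildly liberal at 15 per arm (about 0.04–0.08 in simulation). Subjects who leave before Day 7 contribute nothing to the model.

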9.1.1.2. Adverse Event (AE) and Prior/Concomitant Medications

It is expected that the dates and times for AEs will be complete. For AEs with missing or partially missing start date/time, the following imputation rules will be applied for the determination of treatment-emergent status:

For partial start date/time:

- If the year is unknown, then the date will be assigned the date and time of study treatment.
- If the year is known to be different from the year of the first dose, then missing month and day will be imputed as the first month and first day of the month.
- If the year is known to be the year of the first dose,
 - a) If the month is unknown or is the same as the month of the first dose, then the missing month and day will be imputed by the month and day of the first dose.
 - b) If the month is known to be different from the month of the first dose, then the missing day is imputed as 01 (first day of the month).

The same missing data handling techniques will be used for prior/concomitant medications.

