The total duration of study follow-up will be 12 months after the iovera^{\circ} or RFA procedure. Adverse device effects, serious adverse device effects, adverse events (AEs), and serious adverse events (SAEs) will be recorded from the time the study ICF is signed through Day 360 (± 7 days). Any concomitant medications used to treat AEs through Day 360 (± 7 days) will also be recorded.

Statistical Methods:

As the aim of this pilot study is not to assess effectiveness or efficacy, formal hypothesis testing will not be determined, and sample size will not be calculated based on desired statistical power to detect a treatment effect.

A total of 30 subjects are planned for this pilot study, with 15 randomized to each of the 2 study groups.

Descriptive statistics (number of subjects, mean, SD, median, minimum, and maximum) will be provided for continuous data. Tabulations (number and percentage of subjects) by category will be provided for categorical data. Safety data will be summarized descriptively by treatment groups and overall, and no statistical testing for comparison of treatment groups will be performed for safety variables.

Day 180 Visit

±5d

X X

> → X

	Screen Visit	ioveraº /RFA	24h to 144h	Day 7 Call	Day 15 Call	Day 30	Day 60 Call	Day 90 Call	Day 120	Day 150
		treatment	post-block	Can	Can	Visit	Call	Can	Can	Call
			Call							
Time	≤30 days pre-	Day 1	±4h	±2d	±3d	±5d	±5d	±5d	±5d	±5d
Window	block	-								
Obtain signed ICF	Х									
Assess/confirm eligibility	Х	Х								
Record demographics and baseline characteristics	Х									
Record/update medical and surgical history	Х	Х								
Record/update prior/concurrent medications and therapies	Х	Х								
Measure vital signs ¹	Х	Х								
Perform physical examination per standard of care	Х									
Perform neurological examination per standard of care	Х									
Record NRS pain intensity scores (pain "right now") ²	•									
Record history of workers' compensation, personal injury,	v									
SSDI, or other litigation related to the spine	Λ									
Record NRS pain intensity scores (worst / average pain over	х		-							
24h)							37	37	37	
Administer the Oswestry Disability Index	X					X	Х	X	X	X
Administer the PGIC						X	X	X	X	X
Administer iovera ^o /RFA treatment, record start & stop times		Х								
of procedure		v								
Capture radiographic images		X								
Record concomitant medications (including opioids and										
Depend subject satisfaction with pain management						v	v	v	v	v

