9.6.1. Adverse Events

Adverse events will be coded using the Medical Dictionary for Regulatory Activities (MedDRA v 26.1) or more recent version.

A treatment related adverse event will be considered a TEAE if it starts on/after the time of study (iovera^o or RFA) treatment. If an AE has a partial onset date and time, the imputed start dates will be used to determine treatment-emergence (**Section 9.1.1.2**).

All summaries of AEs will include AEs that occur after the start of iovera^o treatment. Events that start prior to iovera^o treatment will be identified in listings only.

AEs will be summarized using subject incidence table. An overview of AEs will be presented. This table will include n (%) of subjects with:

- Any TEAE
 - Maximum severity: Mild
 - Maximum severity: Moderate
 - Maximum severity: Severe
- At least one related TEAE
- At least one serious TEAE
- Subjects discontinued due to a TEAE
- Serious treatment-emergent adverse events (TESAEs)
- Died on study.

Additionally, n (%) are calculated based on the number of unique subjects within each MedDRA category (e.g., preferred term) by treatment group. A subject reporting multiple events of the same category will be counted only once for that category. For summary purposes, AE relationship to the iovera^o or RFA will be grouped into “Unrelated” for “unrelated” or “unlikely related” and “Related” for “possible”, “probably”, or “definite”. For subjects with more than one event coded to the same PT, the subjects will be counted for the categories with the strongest relationship and the greatest severity. The following subject incidence tables will be presented:

- TEAEs by PT (Preferred Term) sorted by the decreasing order of subject incidence in the combined group
- TEAEs by SOC (System Organ Class) and PT sorted alphabetically
- TEAEs treatment-related by SOC and PT
- TEAEs by severity and by SOC and PT

- TESAEs by SOC and PT.

A data listing will be provided for all AEs. Included in the listing are the reported term, PT, SOC, TEAE and TESAE flag, study day when AE starts, duration, relationship to treatment(s), severity, action taken, outcome, and seriousness category.

Separate data listings will be provided for subjects who experience SAEs and die on study.

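### Certain partial AE start dates are set to the treatment date without checking the stop date, so an event recorded as over before treatment is counted as a TEAE

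*SAP*

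**What the plan says.** **Collection.** The Protocol (Safety Assessments and Safety Endpoints) states that adverse events and device effects "will be recorded from the time the study ICF is signed through Day 360". Under Duration of Subject Participation, up to 30 days may separate consent from the procedure. Events that both begin and end before treatment can therefore be in the database.

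**Imputation.** SAP 9.1.1.2 opens with "It is expected that the dates and times for AEs will be complete". For incomplete start dates, "the following imputation rules will be applied for the determination of treatment-emergent status":

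- Year unknown: "If the year is unknown, then the date will be assigned the date and time of study treatment".
- Year known and different from the treatment year: missing parts become the first month and first day.
- Treatment year, rule a) states: "If the month is unknown or is the same as the month of the first dose, then the missing month and day will be imputed"; the values filled in are those of the treatment date.
- Treatment year, rule b) states: "If the month is known to be different from the month of the first dose, then the missing day is imputed as 01".

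The section ends by applying the same approach to prior and concomitant medications. The stop date is not mentioned there or elsewhere in the SAP.

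**Use.** SAP 9.6.1 treats an AE as treatment-emergent by timing if it starts at or after study treatment. For partial onsets, "the imputed start dates will be used to determine treatment-emergence". Events starting before treatment appear in listings but not in summary tables. The AE listing shows the TEAE flag, the study day of onset and the duration, with no formula for duration.

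**The concern.** Assigning the treatment date when nothing else is known is a sensible conservative default, because an AE that might have followed the procedure is then not lost from the TEAE tables. It stops being sensible when the record shows that the event ended before the procedure. There the rule overrides a known fact, and the result contradicts the timing criterion in SAP 9.6.1.

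Safety is part of the primary objective, and TEAE incidence is the Protocol's safety endpoint. With 15 planned per arm, one misplaced subject is visible in a table. The error can fall in either arm, so it is not reliably conservative for the comparison of the two.

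**Working it through.** The plan gives no figure on this point, so there is none to reproduce. The check applies the SAP 9.1.1.2 rules as written, then the SAP 9.6.1 criterion (imputed start at or after treatment = TEAE).

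**1. One worked example (illustrative dates).** Treatment on 20 March 2023; AE from 6 to 9 March 2023, with the stop date recorded.

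| Start date as recorded | Rule | Start used | Classified |
|---|---|---|---|
| 6 March 2023 | none needed | 6 March | pre-treatment (correct) |
| March 2023, day missing | a) | 20 March | TEAE (wrong) |
| 2023, month and day missing | a) | 20 March | TEAE (wrong) |
| year unknown | first rule | 20 March | TEAE (wrong) |

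In the last three rows the start used is 11 days after the recorded stop. By contrast, an event recorded only as February 2023 is imputed to 1 February under rule b) and correctly stays pre-treatment.

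**2. How much of the pre-treatment period is exposed, given a partial date.** Assumptions: the event starts uniformly over the *W* days before treatment, and treatment falls on any day of a 365-day year with equal chance. The Protocol maximum is *W* = 30; 7 and 14 are shown for shorter gaps.

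- Day only missing. For treatment on day *d* of a month, the share of the *W* days in the same month is min(*d* − 1, *W*)/*W*. For *W* = 30, summing over a month gives 465/30 = 15.5 (31 days), 435/30 = 14.5 (30 days) or 378/30 = 12.6 (28 days). Over the year: (7 × 15.5 + 4 × 14.5 + 12.6)/365 = 179.1/365 = 49%.
- Month and day missing. Only starts in the previous calendar year escape, so the share is 1 − [(*W* + 1)/2]/365. For *W* = 30: 1 − 15.5/365 = 96%.
- Year unknown. Always sent to the treatment date.

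| Missing part | *W* = 7 | *W* = 14 | *W* = 30 |
|---|---|---|---|
| Day only | 87% | 75% | 49% |
| Month and day | 99% | 98% | 96% |
| Year | 100% | 100% | 100% |

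These shares are conditional on that part of the date being missing. They are not the probability of an error. The documents give no missing-date rate, so an expected number of cases cannot be calculated.

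**3. Effect of one case.** SAP 9.6.1 counts each subject once per category. In an arm of 15:

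- subject has no genuine TEAE in that row: +1/15 = +6.7 percentage points;
- subject already has one in that row: +0.

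**4. With a stop-date condition.** If the treatment date is imputed only when the stop date is missing or not before treatment, none of the events in question is flagged: 0% in every cell of the table above.

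**The case against.** The strongest case on the other side is that this is a rare corner of a conservative rule. The error needs three things together: an AE in a period of at most 30 days, a start date incomplete in one of the three named patterns, and a stop date known to precede treatment. The SAP expects complete dates. An unknown year is improbable for an event that arose and ended within those 30 days, so the realistic route is rule a) with only the day missing. Safety is descriptive, without testing between groups, and every AE is listed individually. All of this stands, and it is why the point is minor. It does not make the rule right when it is used.

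A reader might also infer more than the documents support:

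- *That listed durations become negative.* SAP 9.1.1.2 limits the imputation to deciding treatment-emergent status, and no duration formula is given. A negative value would appear only if duration uses the imputed start. Otherwise the listing would show a TEAE flag on an event that stopped before treatment.
- *That each case adds 6.7 points.* This is a ceiling. After an invasive procedure and 360 days of follow-up, the subject may already be counted.
- *That the event is attributed to cryoneurolysis or RFA.* The Protocol's causality scale allows a relationship to be ruled out on timing, so such an event would normally be assessed as unrelated. It would enter the related-TEAE table only if the relationship were blank, because SAP 9.1.1.3 then assigns the strongest category.
- *That the visit of first recording could settle the matter.* No case report form is supplied, and neither document shows that this item is captured. A stop date is on firmer ground, since the listed duration implies one.

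**Conclusion.** The point holds as a minor error in a stated rule. For an AE with an unknown start year, an unknown month in the treatment year, or an unknown day in the treatment month, a recorded stop before treatment does not prevent the event from being counted as a TEAE. This follows from SAP 9.1.1.2 and 9.6.1 read together, with no outside assumption. Its size is at most 6.7 percentage points per case in an any-TEAE or preferred-term row, based on 15 planned subjects per arm. The frequency is unknown but should be low. The default itself is reasonable when the stop date is missing or falls on or after treatment; only the missing exception needs correcting.

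**What to change.** Add to SAP 9.1.1.2, ahead of the imputation rules:

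> Where the recorded stop date, complete or partial, shows that the event ended before study treatment, the event is not treatment-emergent and the treatment date is not imputed as its start. In all other cases the rules below apply.

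A partial stop date that leaves the order open, such as the treatment month with no day, stays under the current rule.

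Apply the same condition to prior and concomitant medications. They use the same rules, so a drug stopped before treatment could otherwise be classed as concomitant. In SAP 9.6.1, state whether listed AE durations use imputed or only recorded dates.

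The cost is a short SAP edit and one programming condition, made before database lock. It needs no protocol change and no new data, provided stop dates are recorded, as the listed duration implies.
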